Clinical Investigation Plan

CIP Reference No.:2018-GI (OEKG) -01. The **SAMISEN** study - Final Version 02 - Date 23th April 2019

The main objective of the SAMISEN study is to assess the performance and safety of diagnostic and therapeutic procedures with the newly designed Olympus Motorized Spiral Enteroscope (INTESTINAL VIDEOSCOPE OLYMPUS PSF-1 and SINGLE USE POWERSPIRAL TUBE DPST-1) system in combination with the motor control unit (POWER SPIRAL CONTROL UNIT PSCU). All Serious Adverse Events (SAE) observed in this study will be documented so the overall SAE rate as well as the number of individual types of complications (bleeding, pancreatitis etc.) can be calculated.

The very recent publication of Rondonotti (Rondonotti et al. 2018) for device-assisted enteroscopy for diagnosis and treatment of small-bowel disorders represents an excellent source for comparison. Hence this study is designed as a prospective study without control group. The resulting SAE rate will be compared to the historical data from this ESGE Technical Review (Rondonotti et al. 2018).

The performance will be characterized by calculating the Diagnostic and Therapeutic Yield, Total Procedure Time, time needed for Therapeutic Intervention, Total Small Bowel Enteroscopy Rate and user feedback on device handling.

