3.1.2 Randomization and Blinding or Assignment of Investigational Device

SAMISEN is designed as a prospective single-arm trial without control group or randomization. All subjects enrolled will undergo at least one procedure with the Motorized Spiral Endoscope (PowerSpiral). There may be a second (optional) procedure depending on investigator's discretion usually because the region of interest could not be reached during the first endoscopy. Subsequent endoscopic procedures are often characterized by a switch in direction (a first antegrade route may be followed by a second retrograde approach or vice versa). From a study perspective and because only part of the subjects will receive a second procedure this additional procedure is called "optional" to indicate that it is not required by protocol but will only be performed if considered necessary by the treating investigator.

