3.1.3 Variables in the Clinical Investigation

It is a prospective and observational Registry without any additional procedure beyond clinical practice. The small-bowel enteroscopy has to be performed according the medical standard. Serious Adverse Events (SAE) and Device Deficiencies (DD) must be documented.

The main safety endpoint is a combined one, capturing all SAEs / DDs captured during the study period. The definition is:

- **Safety:** Incidence (% of subjects) and frequency (no. of subjects) of device or procedure related Serious Adverse Events (SAEs) and Device Deficiencies (DD) observed during/after the procedure.

As main efficacy endpoint we will determine in how many cases the suspected anatomical target lesion can be reached. The definition is:

- **Diagnostic Yield:** Defined as the percentage of procedures that either confirmed a diagnosis from previous studies, or established a new definitive diagnosis at the anatomical location identified in previous studies or findings that could explain the clinical symptoms (Sethi et al. 2014; Prachayakul et al. 2013; Lenz, Roggel, and Domagk 2013; Sanaka et al. 2012).

Clinical Investigation Plan

CIP Reference No.:2018-GI (OEKG) -01. The **SAMISEN** study - Final Version 02 - Date 23th April 2019

Further efficacy endpoints cover performance aspects of the device. The definitions are:

- **Therapeutic Yield:** Defined as the percentage of patients with any endoscopic intervention / therapy with the exception of biopsies. (Sethi et al. 2014; Prachayakul et al. 2013; Sanaka et al. 2012).
- **Total procedure time:** the time from oral (anal) insertion until withdrawal of the device.
- **Total therapeutic intervention time:** The part of the procedure dedicated to therapeutic maneuvers (biopsies will not be considered here).
- **Total small bowel enteroscopy rate:** Defined as complete evaluation of the small bowel either with a single approach or combined anterograde and retrograde approach (if complete small bowel enteroscopy is intended anyway (Committee et al. 2015; Gerson et al. 2015).
- **User feedback** and judgment of handling characteristics and other aspects.

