- Discontinuation of Anticoagulant therapy prior / during the procedure
- Provide information about the planned small-bowel enteroscopy
 - Main indication for the planned small- bowel enteroscopy procedure.
 - Select if a capsule endoscopy, CT/MRT enteroclysm or another imaging technique was performed previously.
 - Describe if there were any positive findings during the previous diagnostic workup (e.g. if a bleeding was detected).
- Describe the initially planned PowerSpiral approach
 - Is a total enteroscopy of the small-bowel planned?
 - Start with antegrade procedure and add a retrograde one if unsuccessful or incomplete *or*
 - Start with retrograde procedure and add an antegrade one if the initial procedure is unsuccessful or incomplete *or*
 - Perform a combined antegrade and retrograde examination during a single session.

At visit V2 and V3 (optional):

- At this visit the PowerSpiral enteroscopy will be performed.
- Enter the date and name of the responsible investigator who performs the enteroscopy.
- Enter the total procedure time (“scope-in, scope-out”) measured from initial enteroscope introduction through the bite block to final enteroscope withdrawal through the bite block (minutes) (for antegrade approach) or crossing the linea dentata of the anus in case of a retrograde approach.
- Provide information about the kind of staff and number persons needed for this enteroscopy.
- Select if an antegrade, retrograde or combined enteroscopy was performed.
- Select if a general anesthesia or sedation is used.
- Select which part of the small-bowel was reached.
- Answer if the findings of the previous imaging examinations were confirmed or not.

Clinical Investigation Plan

CIP Reference No.:2018-GI (OEKG) -01. The **SAMISEN** study - Final Version 02 - Date 23th April 2019

- Answer if there was any therapeutic intervention performed. If yes please specify in the free text section.
- Enter the time needed for any therapeutic intervention. If several slots for therapeutic interventions occurred, please add the time needed for each therapeutic slot and enter the total duration in minutes.
- Answer if any Serious Adverse Events occurred during the enteroscopy procedure.
- Document the final diagnosis after the enteroscopy
- Answer the following questions:
 - Was the therapeutic intervention successful and were all planned therapeutic aim(s) achieved?
 - Was the initial therapeutic management plan modified during the procedure?

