2.4 Primary and secondary variables

Primary efficacy variable:

The rate of serious adverse events during and after enteroscopy will constitute the primary endpoint for this study.

Secondary efficacy variables:

- Reaching the anatomical region of interest: The rate of successfully reaching the suspected anatomical target region (either by antegrade or by retrograde route) compared to all attempts represents the endpoint 'anatomical success rate'.
- Therapeutic yield: Defined as the percentage of patients with any endoscopic intervention / therapy with the exception of biopsies. (Sethi et al. 2014; Prachayakul et al. 2013; Sanaka et al. 2012)
- Total procedure time: Period in minutes needed to complete the procedure.
- Total therapeutic intervention time: Period in minutes dedicated to therapeutic intervention(s).
- Total small bowel enteroscopy rate: Defined as complete evaluation of the small bowel either with a single approach or combined anterograde and retrograde approach (if complete small bowel enteroscopy is intended anyway (Committee et al. 2015; Gerson et al. 2015).
- Diagnostic Yield (i.e. diagnosis, that explains findings from previous imaging or establishes a new diagnosis, that could explain clinical symptoms, that indicated PSE)
- User feedback and judgment of handling characteristics and other aspects: User feedback and assessment of handling characteristics and other logistical aspects regarding:
 - Handling of PowerSpiral
 - Instrument insertion of PowerSpiral
 - Precision of positioning during therapy of PowerSpiral
 - Time needed for procedure of PowerSpiral
 - Staff and resource needed for procedure of PowerSpiral
- Serious adverse events (PS product related)
- Adverse events during enteroscopy procedure and adverse events (PS product related)

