3.6 Efficacy Analysis

The following efficacy analyses will be performed based on the cITT population and on the ITT population as sensitivity analysis:

- The anatomical success rate (number of cases in which the suspected anatomical region is reached compared to all attempts) will be computed alongside with its 95% Clopper-Pearson confidence interval.
- The therapeutic yield (percentage of patients with any endoscopic intervention/therapy with exception of biopsies) will be presented alongside its 95% Clopper-Pearson confidence interval.
- The total procedure time (period in minutes needed to complete the procedure) will be summarized descriptively.
- The total therapeutic intervention time will be summarized descriptively.
- The total small bowel enteroscopy rate (number of complete evaluations of the small bowel divided by all attempts to reach the small bowel) will be computed alongside its 95% Clopper-Pearson confidence intervals.
- The outcomes for the items in the user feedback for the judgement of handling characteristics and other aspects will be tabulated in frequency tables.
- Diagnostic Yield (i.e. diagnosis, that explains findings from previous imaging or establishes a new diagnosis, that could explain clinical symptoms, that indicated PSE)
 - Diagnostic Yield is defined as the difference of proportion of patients for which a diagnosis was made and the proportion of patients with prior positive imaging (VKE, MRI, other)

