3.8 Other Analyses

None.

3.9 *List of all tables / listings / figures with their location in Clinical Study Report*

DT = Descriptive statistics table with n, mean, standard deviation, median, 25th and 75th percentiles, minimum and maximum

FT = Frequency table with absolute and relative frequencies, for the primary endpoint, 95% confidence intervals will be added

GL = General listing of parameters with patient ID, center, analysis population in each listing.

Description of table / figure / listing	Type
Tables	
11.1.1 Patient Disposition - All Enrolled Population Reference: annCRF page 5 Parameters: Patients with entries Analyses: absolute and relative frequencies	FT
11.1.2 Analysis Populations - All Enrolled Population Reference: None Parameters: Analyses populations (SAF, cSAF, ITT, cITT) Analyses: absolute and relative frequencies	FT
11.1.3 In- and Exclusion criteria fulfilled? - SAF and cSAF Reference: annCRF page 5-6 Parameters: Categorical parameters Analyses: absolute and relative frequencies	FT
11.1.4 Visit Schedules - SAF and cSAF Reference: annCRF Page 3 Parameters: Median time from enrollment to discharge Analyses: Descriptive analyses	DT
11.1.5.1 Demographics and Baseline Characteristics - Continuous Parameters - SAF and cSAF Reference: SAP chapter 3.5 Parameters: Age Analyses: Descriptive analyses	DT
11.1.5.2 Demographics and Baseline Characteristics - Categorical Parameters - SAF and cSAF Reference: SAP chapter 3.5 Parameters: Sex Analyses: absolute and relative frequencies	FT
11.1.6 Previous Abdominal Surgery - SAF and cSAF Reference: annCRF page 10-11 Parameters: Previous abdominal surgery, etc. Analyses: absolute and relative frequencies	FT
11.1.7.1 Information About Small-Bowel Enteroscopy - Listing of Indication - SAF and cSAF Reference: annCRF page 12 Parameters: Indication Analyses: Listing of freetext	GL
11.1.7.2 Information About Small-Bowel Enteroscopy - SAF and cSAF Reference: annCRF page 12 Parameters: Categorical parameters on information about planned small-bowel enteroscopy Analyses: absolute and relative frequencies	FT

Description of table / figure / listing	Type
11.1.7.3 Initially Planned Procedure with PowerSpiral - SAF and cSAF Reference: annCRF page 12-13 Parameters: Categorical parameters Analyses: absolute and relative frequencies	FT
11.1.7.4 Initially Planned Procedure with PowerSpiral - Listing of Freetext - SAF and cSAF Reference: annCRF page 12-13 Parameters: Freetext Analyses: Listing of freetext	GL

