11.1.7.5 Procedure with PowerSpiral - Categorical Parameters - SAF and cSAF Reference: annCRF page 16-17 Parameters: Procedure with PowerSpiral, Procedural information Analyses: absolute and relative frequencies	FT
11.1.7.6 Procedure with PowerSpiral - Continuous Parameters - SAF and cSAF Reference: annCRF page 16-17 Parameters: Length of procedure, Time to reach deepest point of enteroscopy, Time score out Analyses: descriptive statistics	DT
11.1.7.7 Therapeutic Interventions - Listing of Comments - SAF and cSAF Reference: annCRF page 17 Parameters: Freetext, Start and Stop time of intervention by patient Analyses: Listing of freetext	GL
11.2.1 Assessment After Procedure - Categorical Parameters - ITT and cITT Reference: annCRF page 18 Parameters: Categorical parameters Analyses: absolute and relative frequencies	FT
11.2.2 Assessment After Procedure - Listing of Comments - ITT and cITT Reference: annCRF page 18 Parameters: Freetext Analyses: Listing of freetext	GL
11.2.3 Evaluation of Procedure - Categorical Parameters - ITT and cITT Reference: annCRF page 19-20 Parameters: Handling, instrument insertion, Precision, time needed, staff and resources needed Analyses: absolute and relative frequencies by category (worse, similar, better)	FT
11.2.4 Evaluation of Procedure - Diagnostic Yield - ITT and cITT Reference: SAP section 3.6 Parameters: positive imaging prior to procedure, information whether a diagnosis was made with PSE Analyses: absolute and relative frequencies	FT

Description of table / figure / listing	Type
11.3.1.1 Adverse Events during procedure - SAF and cSAF Reference: annCRF page 17 Parameters: Trigger question on AEs Analyses: absolute and relative frequencies	FT
11.3.1.2.1 Adverse Events by category - SAF and cSAF Reference: annCRF page 23 Parameters: Adverse event category Analyses: absolute and relative frequencies	FT
11.3.1.2.2 Serious Adverse Events by category - SAF and cSAF Reference: annCRF page 23 Parameters: Adverse event category Analyses: absolute and relative frequencies	FT
11.3.1.3 Adverse Events by category - Listing of other AEs - SAF and cSAF Reference: annCRF page 23 Parameters: Freetext Analyses: Listing of Freetext	GL
11.3.1.4.1 Adverse Events - Relatedness - SAF and cSAF Reference: annCRF page 23 Parameters: Relatedness Analyses: absolute and relative frequencies	FT

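### SAP 3.6 computes diagnostic yield as diagnosis rate minus prior-positive-imaging rate, so confirmed findings cancel and the value can be zero or negative

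*SAP*

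**What the plan says.** The protocol's trial summary and section 3.1.3 treat diagnostic yield as a success proportion: "Defined as the percentage of procedures that either confirmed a diagnosis from previous studies, or established a new definitive diagnosis", with explanatory findings also counted. In 3.1.3 the definition stands directly under the sentence introducing the main efficacy endpoint. Section 1.2 says that "The performance will be characterized by calculating the Diagnostic and Therapeutic Yield" and several other measures. Section 4.1.2, the efficacy list in the statistics chapter, leaves diagnostic yield out.

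SAP 2.4 lists it as a secondary variable and describes it as a "diagnosis, that explains findings from previous imaging or establishes a new diagnosis, that could explain clinical symptoms, that indicated PSE". SAP 3.6 repeats that description, then adds a sub-bullet under which the measure is "defined as the difference of proportion of patients for which a diagnosis was made and the proportion of patients with prior positive imaging".

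In the SAP 3.9 list of outputs, Table 11.2.4 refers back to section 3.6. Its parameters are "positive imaging prior to procedure, information whether a diagnosis was made with PSE", shown as absolute and relative frequencies. The key for frequency tables says that "for the primary endpoint, 95% confidence intervals will be added".

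**The concern.** The sub-bullet contradicts the protocol, SAP 2.4 and its own parent bullet. Each of those counts a diagnosis that confirms or explains a pre-procedure finding as a success. The subtraction removes exactly those patients, and it counts against the device every imaging-positive patient in whom no diagnosis was made. The unit also moves from procedures to patients, and no reason is given for either change.

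At stake is the figure that will carry the name diagnostic yield. The protocol uses that quantity to characterise performance. A value near zero or below could not be read as a yield or set beside a yield defined as a proportion. It would also depend heavily on how many patients were referred with positive imaging, which is not a property of the device.

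**Working it through.** The documents give no expected diagnostic yield, so there is no planned figure to reproduce. The check is algebra, followed by illustrations with assumed rates.

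**Algebra.** Classify N patients by prior imaging and by diagnosis at PowerSpiral enteroscopy:

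| | Diagnosis made | No diagnosis |
|---|---|---|
| Prior imaging positive | a | c |
| Prior imaging not positive | b | d |

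Assume one procedure per patient, that every diagnosis made is a success under the protocol, and that both proportions have denominator N.

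- Protocol-type yield = (a + b)/N, between 0 and 100%.
- SAP 3.6 value = (a + b)/N − (a + c)/N = (b − c)/N, between −100 and +100 points.

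Cell a, the confirmed findings, cancels. A confirmed patient contributes 0, an imaging-positive patient without a diagnosis contributes −1, and only a diagnosis without prior positive imaging contributes +1. If all 245 patients were imaging-positive and all were diagnosed, the yield would be 100% and the SAP value 0. The two measures agree only when no patient has prior positive imaging.

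**Dependence on case mix.** Let p be the imaging-positive share, r₁ the diagnosis rate after positive imaging and r₀ the rate otherwise.

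- Yield = r₁p + r₀(1 − p)
- SAP value = yield − p = r₀(1 − p) − (1 − r₁)p

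| p | Yield, r₁ = 85%, r₀ = 50% | SAP value | Yield, r₁ = r₀ = 75% | SAP value |
|---|---|---|---|---|
| 30% | 60.5% | +30.5 points | 75% | +45 points |
| 50% | 67.5% | +17.5 points | 75% | +25 points |
| 70% | 74.5% | +4.5 points | 75% | +5 points |
| 90% | 81.5% | −8.5 points | 75% | −15 points |

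In the first scenario the slopes in p are r₁ − r₀ = +0.35 for the yield and r₁ − r₀ − 1 = −0.65 for the SAP value, so the two move in opposite directions. In the second, the yield is constant and the SAP value changes with referral mix alone.

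**Counts.** Take N = 245, the number the protocol expects to analyse (section 3.3.6), with 172 imaging-positive. Assume a = 146, c = 26, b = 36 and d = 37.

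- Yield = (146 + 36)/245 = 182/245 = 74.3%; 95% Clopper-Pearson interval 68.3 to 79.6%.
- SAP value = (36 − 26)/245 = +4.1 points.

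Other assumed cells for the same N:

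| a, b, c, d | Yield (95% CI) | SAP value |
|---|---|---|
| 196, 0, 0, 49 | 80.0% (74.4 to 84.8) | 0.0 points |
| 150, 30, 46, 19 | 73.5% (67.5 to 78.9) | −6.5 points |
| 196, 0, 49, 0 | 80.0% (74.4 to 84.8) | −20.0 points |
| 60, 110, 10, 65 | 69.4% (63.2 to 75.1) | +40.8 points |

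**Unit.** Protocol 3.1.2 says a second procedure is done "usually because the region of interest could not be reached during the first endoscopy". A patient whose first session fails and whose second succeeds counts 1 of 2 per procedure and 1 of 1 per patient. The choice of unit therefore changes the result, and procedures within a patient are not independent.

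**Interval.** SAP 3.6 names a Clopper-Pearson interval for anatomical success, therapeutic yield and total enteroscopy rate. It names none for diagnostic yield.

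**The case against.** The best defence is that the difference was meant as an incremental yield over imaging, and that little is lost because Table 11.2.4 shows both components. It is true that the patient-level diagnosis rate stays visible and that the listed table does not itself subtract. But no document describes an incremental measure, and section 3.6 calls the difference diagnostic yield. The table's listed parameters also do not include whether earlier findings were confirmed.

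Four narrower points deserve an answer.

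- **Denominators.** Section 3.6 states none. If the imaging proportion were taken only among patients who had imaging, the cancellation would not be exact. In the worked example, if 215 of the 245 had been imaged (an assumption), the value would be 182/245 − 172/215 = 74.3% − 80.0% = −5.7 points. It can still be zero or negative, and the missing denominator is a further gap.
- **Intervals.** SAP 3.5 promises confidence intervals where appropriate. That sentence is in the section on demography and study procedures, so its reach is arguable. The firm statement is that no interval is named for this rate.
- **Rank.** Protocol 3.1.3 describes the main efficacy endpoint as reaching the target lesion and then defines diagnostic yield, while SAP 2.4 makes diagnostic yield secondary. The rank is unclear, and the finding does not rest on it.
- **Inputs.** The opposite movement occurs only when diagnosis is more frequent after positive imaging, and the registry will have one case mix, not four. This limits the illustration but not the algebra.

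**Conclusion.** The concern holds: the rule in SAP 3.6 is wrong as written. With a common patient denominator, it removes confirmed findings from a measure that the protocol and SAP 2.4 define to include them. In the illustrations with some prior positive imaging, protocol-type yields of 60.5 to 81.5% correspond to SAP values between −20.0 and +45 points. The size in this study cannot be predicted, since the share with positive imaging and the diagnosis rates are not given. Prior imaging findings are a listed indication for inclusion, so the cancelled cell is unlikely to be empty.

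The consequence is confined to a descriptive estimate. Protocol 4.1.2 rules out hypothesis tests for efficacy, and neither the sample size nor the primary safety analysis uses this endpoint. It should be corrected before analysis, but it does not threaten the study's main conclusion.

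**What to change.** - Delete the difference sub-bullet in SAP 3.6.
- Define diagnostic yield as the protocol does: procedures that confirmed the earlier diagnosis, established a new definitive one or produced findings that could explain the symptoms, divided by procedures performed.
- Add a per-patient rate, counting success in any session, with a 95% Clopper-Pearson interval, and state both denominators.
- If the gain over imaging is of interest, show prior imaging by PowerSpiral diagnosis as a two-by-two table under a different name.

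The first two changes restore agreement with the protocol; the other two are recommended additions. The cost is SAP wording and reprogramming of Table 11.2.4. Protocol 3.4.2 already instructs sites: "Answer if the findings of the previous imaging examinations were confirmed or not". It also collects the indication and the final diagnosis. Whether a new diagnosis explains the symptoms may have to be derived from those two items, under a rule written into the SAP beforehand.
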